#### 16.6 Medical coding

Medical coding will be performed by trained personnel at CTC. AEs and medical/surgical history verbatim terms will be coded using the Medical Dictionary of Regulatory Activities (MedDRA; latest version available at start of coding). Prior and concomitant medications will be coded according to the World Health Organization (WHO) Anatomic Therapeutic Chemical (ATC) classification system. All coding will be approved by Sponsor prior to database lock.

#### 16.7 Database lock

When all data have been entered, all external data have been received and discrepancies solved, clean file will be declared, the database will be locked, the randomisation code will be broken and the data will be analysed.

#### **17 STATISTICAL METHODS AND DETERMINATION OF SAMPLE SIZE**

The principal features of the statistical analysis to be performed are described in this section. A more technical and detailed elaboration of the principal features will be presented in a separate Statistical Analysis Plan (SAP), which will be signed and approved prior to database lock.

Analyses of the primary and secondary endpoints will be performed by CTC.

#### 17.1 General

Continuous data will be presented in terms of evaluable and missing observations, arithmetic mean, SD, median, minimum and maximum value.

Categorical data will be presented as counts and percentages and by means of absolute and relative frequencies where applicable.

All descriptive statistics will be presented by part, assigned treatment (dose cohort or placebo) and by assessment time where applicable.

Individual subject data will be listed by part, treatment, subject number, and, where applicable, by assessment time.

All descriptive summaries and statistical analyses will be performed using SAS Version 9.4 or later (SAS Institute, Inc., Cary, NC).

The baseline measurement will be defined as the latest measurement prior to the first administration of the IMP.

No imputation of missing data will be performed.

#### 17.2 Determination of sample size

No formal sample size calculation has been performed for this trial. The proposed sample size is considered sufficient to provide adequate information for the trial objectives.

Approximately 144 subjects will be screened to achieve a total of 72 randomised and dosed subjects. The number may increase if additional dose cohorts need to be investigated and/or if recommended by the iSRC.

#### 17.3 Analysis data sets

#### 17.3.1 Full analysis set

The Full Analysis Set (FAS) will consist of all subjects who have been randomised and received at least one dose of IMP and who has at least one post-baseline assessment of data. The FAS will be used for all safety and PD evaluations.

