# 9.3 Number of subjects

[figure not shown]
Approximately 160 subjects will be screened (approximately 96 for Part A and 64 for Part B) to achieve a total of 80 randomised and dosed subjects. The number may increase if additional dose cohorts need to be investigated and/or if recommended by the iSRC.

Part A: 48 subjects will be randomised and dosed in 6 cohorts (Cohorts A1 to A6, each of 8 subjects with 6 subjects receiving C106 and 2 subjects receiving placebo).

Part B: 32 subjects will be randomised and dosed in 4 cohorts (Cohorts B1 to B4, each of 8 subjects with 6 subjects receiving C106 and 2 subjects receiving placebo).

If indicated by emerging data and recommended by the iSRC, 2 cohorts (8+8 subjects) may be added to Part A and 1 cohort (8 subjects) may be added to Part B. In such cases, and to account for potential dropouts, additional subjects might be included in the trial.

For replacements of subjects who discontinue from the trial, see Section 9.8.

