#### 17.3.2 Pharmacokinetic analysis set

The Pharmacokinetic analysis set (PKAS) will consist of all subjects who received at least one dose of the trial drug and provided an plasma concentration data and who have no AEs or

protocol deviations judged to affect the PK analysis. Individual PK values may be excluded from the analysis as specified in the SAP.

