## 17.5 Analysis of primary endpoints

#### 17.5.1 Adverse events

An overview of all AEs, including SAEs, intensity, and relationship to IMP will be presented. Incidence of AEs and SAEs will be summarised by SOC and PT by part, cohort, treatment and overall. An overview of any related AEs will be summarised by SOC and PT if considered appropriate.

All AE data will be listed by part, treatment, and subject and include the verbatim term entered by the Investigator.

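### The only safety population requires randomisation and a post-baseline assessment, so a dosed subject can, in rare cases, be left out of the safety tables and denominators

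*Combined protocol and SAP*

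**What the plan says.** Section 17.3 defines two analysis sets.

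- **FAS (17.3.1).** Membership needs randomisation, and the subject must have "received at least one dose of IMP and who has at least one post-baseline assessment of data". On its use the section says: "The FAS will be used for all safety and PD evaluations".
- **PKAS (17.3.2).** "The Pharmacokinetic analysis set (PKAS) will consist of all subjects who received at least one dose of the trial drug", with further conditions on concentration data and on events or deviations affecting PK. It serves the PK analysis only.

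The primary endpoint tables rest on the FAS. Section 17.5.1 states: "Incidence of AEs and SAEs will be summarised by SOC and PT by part, cohort, treatment and overall". Cohorts are small, "each of 8 subjects with 6 subjects receiving C106 and 2 subjects receiving placebo" (Section 9.3).

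Section 17.1 says: "The baseline measurement will be defined as the latest measurement prior to the first administration of the IMP". It also rules out imputation. The protocol does not define what counts as a post-baseline assessment.

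Sections 8.1.1.1, 9.8.5 and 10.5.1 allow dropouts from the food-interaction cohort to be replaced, and every replacement subject receives C106. Section 9.9 describes randomisation only for the 8 subjects of a cohort, as 1:1 for the sentinel pair and 5:1 for the rest. It does not mention replacement subjects.

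**The concern.** The primary objective is safety and tolerability, and the safety results are descriptive, so the counts by cohort are the primary result. The natural denominator is everyone exposed. The FAS adds two conditions to exposure. The post-baseline condition can be met only after dosing, so membership depends on what happens to the subject after the first dose. It suits a change-from-baseline analysis but has no function in an AE incidence table. The randomisation condition has a different effect: it may leave out people who were given C106 by assignment.

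With 6 active subjects per dose, one omission alters the denominator by a sixth. Under Section 9.8.5, dosed subjects in Part A are not replaced outside the food cohort, so the loss would not be made good. If the wording stays open, someone may also have to decide on inclusion after the data have been seen.

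**Working it through.** **Planned denominators.** Section 9.3 gives 6 cohorts of 8 in Part A and 4 cohorts of 8 in Part B.

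- Total: 6 × 8 + 4 × 8 = 48 + 32 = 80, which reproduces the plan's figure ("to achieve a total of 80 randomised and dosed subjects").
- On C106: 6 × 6 + 4 × 6 = 60. On placebo: 2 × 10 = 20.

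Section 17.2 gives a different total: "Approximately 144 subjects will be screened to achieve a total of 72 randomised and dosed subjects". That is 9 × 8, one cohort fewer. It is a separate inconsistency to reconcile and does not affect this point.

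**Who enters the FAS.**

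| Dosed subject | Randomised | Post-baseline assessment | In FAS |
|---|---|---|---|
| Randomised, with an AE record or any post-dose measurement | yes | yes, as the protocol uses the term | yes |
| Randomised, no post-dose record of any kind | yes | no | no |
| Food-cohort replacement assigned to C106 | not stated | yes | depends on the reading |

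**Size, subject with no post-dose record.** Such a subject brings no event to the numerator, so only the denominator changes. For zero events in n subjects the exact two-sided 95% upper limit is 1 − 0.025^(1/n).

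- One cohort, all dosed: 0/6, upper limit 1 − 0.025^(1/6) = 45.9%.
- One cohort, FAS: 0/5, upper limit 1 − 0.025^(1/5) = 52.2%.
- All active subjects: 0/60 (upper limit 6.0%) against 0/59 (6.1%).
- If another subject in the cohort has an event: 1/6 = 16.7% (exact 95% interval 0.4 to 64.1) becomes 1/5 = 20.0% (0.5 to 71.6).

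**Size, replacement subject.** Suppose one of the 6 active subjects in the food cohort leaves after the fasted dose and is replaced. The number exposed to C106 in that cohort is then 6 + 1 = 7. A literal reading of the FAS counts 6. A replacement subject has a full set of post-dose data, so here an event could be lost too: if only that subject had the event, 1/7 = 14.3% would be shown as 0/6.

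**Frequency.** The documents give no rate of very early departure and do not say whether any replacement has been used, so I attach no probability to either case.

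**The case against.** The strongest reply is that the protocol's own usage and monitoring leave almost nobody without a post-baseline assessment.

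- AEs head the list of safety assessments in the synopsis. Table 7.1-1 puts AE reporting and questioning in its assessment column, and Section 11.3.1 sits under the heading for assessments of primary endpoints.
- In Part A, telemetry runs from 30 minutes before dosing to 24 hours after it and is reviewed by the Investigator (Section 11.3.3, Table 8.1-2).
- Section 9.8.4 requires discontinuing subjects always to be asked about AEs, and Visit 3 also applies after early withdrawal.
- AE listings are not expressly restricted to the FAS, the safety committee sees dropout data (Section 8.3.6), and the stopping rules do not refer to the FAS.
- Section 17 leaves technical detail to a separate SAP, which could settle the matter.

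All of this stands, and it defeats a stronger reading that a reader might infer. The first scheduled post-dose PK sample is at 20 minutes, and the first ECG and vital signs are at 40 minutes. One might conclude that a subject who reacts at once and is taken off the schedule would vanish, turning 1/6 with a serious reaction into 0/5. That needs an assessment to mean a scheduled measurement. Section 17.1 uses measurement to define baseline, but nothing restricts the word assessment in Section 17.3.1 in the same way, and the usage above points the other way. A recorded reaction would ordinarily keep the subject in the FAS.

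The reply does not give the post-baseline clause any purpose in a safety analysis, and it does not touch the randomisation condition. The supplied text contains no further definition of a safety set.

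**Conclusion.** The point holds as a defect of definition with a small expected effect. The FAS is the only safety population and is narrower than the set of dosed subjects. A dosed subject without any post-dose record is excluded on any reading, which moves a cohort from 0/6 to 0/5. This is most conceivable in Part B, which has no telemetry. A food-cohort replacement is excluded only if the randomisation condition is taken literally and assignment to C106 does not count as randomisation; the documents do not say.

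The conclusion assumes 6 active subjects per cohort, one affected subject, and no clarification in a SAP text that is not among the documents supplied. The documents do not support a claim that the trial would lose its most important event, or that dose-escalation safety is weakened. This is a free improvement and not a threat to the trial's conclusions.

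**What to change.** In Section 17.3.1 and the SAP, define a safety set of every subject given IMP at least once, with no condition on randomisation or on later data, and use it for all safety summaries. Food-cohort replacements then count without further debate.

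Keep a post-baseline requirement only for the EndoPAT evaluation in cohort B4, where a change from baseline needs both recordings. For laboratory and vital-sign changes no exclusion is needed: Section 17.1 already reports evaluable and missing counts and imputes nothing, so a subject without a post-dose value appears as missing.

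The cost is one or two sentences, settled before database lock. Sample size, assessments and trial conduct are unaffected. If no dosed subject is ever omitted under the present wording, the change alters no result.

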#### 17.3.2 Pharmacokinetic analysis set

The Pharmacokinetic analysis set (PKAS) will consist of all subjects who received at least one dose of the trial drug and provided an plasma concentration data and who have no AEs or

protocol deviations judged to affect the PK analysis. Individual PK values may be excluded from the analysis as specified in the SAP.

#### **17.4 Description of trial population**

## 17.4.1 *Demographics and baseline characteristics*

Descriptive statistics for demographics, weight, height and BMI, will be presented by treatment and cohort. All data will be listed by part, treatment and subject.

#### 17.4.2 *Medical/surgical history and prior/concomitant medication*

Medical/surgical history will be presented by SOC and preferred term (PT). Prior/concomitant medications will be presented by ATC level 3 and 5. All data will be listed by part, treatment and subject.

#### 17.4.3 *Treatment compliance*

Individual dose(s) will be listed by part, treatment and subject.

## 17.5 Analysis of primary endpoints

#### 17.5.1 Adverse events

An overview of all AEs, including SAEs, intensity, and relationship to IMP will be presented. Incidence of AEs and SAEs will be summarised by SOC and PT by part, cohort, treatment and overall. An overview of any related AEs will be summarised by SOC and PT if considered appropriate.

All AE data will be listed by part, treatment, and subject and include the verbatim term entered by the Investigator.

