# Endpoints

### **Primary endpoints**

- Treatment Emergent adverse events (AEs) and serious AEs (SAEs).
- Clinically relevant changes in:
  - 12-lead electrocardiograms (ECGs).
  - Vital signs (blood pressure, heart rate (HR), body temperature and respiratory rate
  - Laboratory safety variables (haematology, coagulation, clinical chemistry, and urine analysis).
  - Physical examination.

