### Part A (SAD):

In Part A, single, oral doses of C106 will be administered in 6 sequential dose cohorts, each of 8 subjects. Within each cohort, subjects will be randomised to receive either C106 (n=6) or placebo (n=2) in the fasted state. The proposed doses are: 5, 30, 60, 180, 240 and 300 mg C106. Up to 2 additional dose cohorts can be explored based on emerging safety, tolerability and PK of the drug, if recommended by the iSRC. The maximum oral dose in Part A will not exceed 480 mg C106.

Subjects will come for 3 visits to the Clinical Research Unit (CRU). Screening (Visit 1) will take place within 4 weeks of the planned dose (Day -28 to Day -1) and will include the subject's signing of the informed consent and an eligibility check. At Visit 2, subjects will reside at the CRU from Day -1 (the day before investigational medicinal product [IMP] administration) until Day 3 for single dose IMP administration, safety, tolerability, and PK assessments. The subjects must fast for at least 10 hours before until 4 hours after the anticipated dosing time on Day 1. During fasting, water, but no other drinks, is allowed as desired. No drinks are allowed for 1 hour before and 1 hour after dosing. The first 2 subjects in each cohort will be dosed in a sentinel fashion, 1 subject will receive C106 and the other will receive placebo as randomised. The subjects will be carefully monitored by clinical staff during and after dosing. Vital signs and ECG will be checked at regular intervals. Ambulatory ECG telemetry will be used for cardiac surveillance up to 24 hours after IMP administration. There is immediate access to equipment, qualified staff and an intensive care unit (ICU) in case of an acute emergency. To give sufficient time for observation of any reactions there will be at least 24 hours before dosing of the remaining 6 subjects, who will be dosed in groups of 3 subjects at least 24 hours apart. A final end-of-trial visit (Visit 3) will take place on Day 7 ( $\pm 2$  days) or after early withdrawal.

Cardiodynamic ECG assessments (collect and store) will be performed in all cohorts (except the first cohort A1) where C106 is given in the fasted state (*i.e.*, not in the fed period of the fasted/fed cohort) and will include serial ECG extractions at baseline (prior to dosing) and at the same time points as PK sampling during the first 24 hours post-dose.

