# 11.3.1.6 Time period and frequency for collecting adverse events

All AEs (including SAEs) will be collected from the signing of informed consent until the end-of-trial visit of each part.

Any AE with start date on the day of IMP administration must be recorded with start time.

At the end-of-trial visit, information on new AEs or SAEs, if any, and stop dates for ongoing events must be recorded as applicable.

Investigators are not obligated to actively seek AEs or SAEs after conclusion of the trial participation. However, if the Investigator learns of any SAE, including a death, at any time after a participant has been discharged from the trial, and he/she considers the event to be reasonably related to the trial intervention or trial participation, the Investigator must promptly notify the Sponsor.

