# 11.3.1.12 Recording adverse events

AEs must be recorded in the AE Log of the eCRF. The Investigator must provide information on the AE, preferably with a diagnosis or at least with signs and symptoms; start and stop dates, start and stop time; intensity; causal relationship to IMP; action taken, and outcome.

If the AE is serious, this must be indicated in the eCRF.

AEs, including out-of-range clinically significant clinical safety laboratory values, must be recorded individually, except when considered manifestations of the same medical condition or disease state; in such cases, they must be recorded under a single diagnosis.

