## 11.3.4 Vital signs

At visits and time points outlined in Table 8.1-1 and Table 8.1-2 (Part I) and in Table 8.1-3, Table 8.1-4 and Table 8.1-5 (Part II), systolic and diastolic blood pressure (BP) and pulse will be measured in supine position after 10 minutes of rest. Respiratory rate will be assessed. Body temperature will be measured using a digital thermometer on Day -1 of each part.

Any vital signs outside the normal ranges will be judged as not clinically significant or clinically significant. The assessment will be recorded in the eCRF. Abnormal post-dose findings assessed by the Investigator as clinically significant will be reported as AEs.

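### The primary endpoint is treatment-emergent adverse events, but Section 17.5.1 tabulates all adverse events, and the single baseline does not fit the fed period of the food-interaction cohort

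*Combined protocol and SAP*

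**What the plan says.** The first primary endpoint in the synopsis is "Treatment Emergent adverse events (AEs) and serious AEs (SAEs"; Table 7.1-1 repeats it. On collection, Section 11.3.1.6 states: "All AEs (including SAEs) will be collected from the signing of informed consent until the end-of-trial visit of each part". Consent is taken at screening, and for Part A the synopsis states: "Screening (Visit 1) will take place within 4 weeks of the planned dose (Day -28 to Day -1". Part B has the same window before its first dose.

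Section 17.5.1 sits under the analysis of primary endpoints. It plans two displays. The first is described as: "An overview of all AEs, including SAEs, intensity, and relationship to IMP will be presented". The second reads: "Incidence of AEs and SAEs will be summarised by SOC and PT by part, cohort, treatment and overall". A summary of related AEs by SOC and PT is optional, and all AEs are listed.

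Section 17.1 gives one baseline for each subject: the last value obtained before that subject's first dose. Sections 17.5.3 and 17.5.4 summarise vital signs and laboratory data as changes from it. Note 2 to Table 8.1-1 gives subjects in the food-interaction cohort two intervention periods with a washout between them. Section 8.1.1.1 sets that washout at a minimum of 5 half-lives and repeats the fasted-period assessments in the fed period.

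**The concern.** The analysis named for the primary endpoint is not an analysis of that endpoint. An AE that starts between consent and first dose in a subject who is later dosed is not treatment-emergent. Even so, the displays in Section 17.5.1 would count it under that subject's assigned treatment. With six C106 subjects and two placebo subjects per cohort, a single such subject visibly changes a cohort's incidence.

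The baseline raises a similar problem in one cohort. A drift in blood pressure or a laboratory value that is already present when a subject returns for the fed dose would be reported as a fed-period change, because the reference value predates the fasted dose. The crossover was chosen for within-subject comparison (Section 8.2), and PK is reported separately for fasted and fed conditions (Section 17.6.1). The safety sections set no fasted or fed period level.

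**Working it through.** The plan gives no figure of its own on this point, so the check compares sections and adds simple arithmetic.

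**Does any section supply an onset rule?**

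1. Section 17.3.1 (full analysis set) removes subjects who were never dosed. It does not remove pre-dose AEs of subjects who were dosed.
2. Section 11.3.1.1 defines an AE in terms of a subject given a medicinal product. This does not act as an onset rule: Section 11.3.1.6 starts collection at consent, and Section 11.3.1.8 has a causality category that can be used for subjects who received no IMP.
3. Section 11.2.6 has a timed rule that separates prior from concomitant medication, including on Day 1. Section 17.5.1 has no counterpart for AEs.
4. Some pre-dose events are kept out by the recording rules. For vital signs, Section 11.3.4 states: "Abnormal post-dose findings assessed by the Investigator as clinically significant will be reported as AEs". Sections 11.3.2, 11.3.3, 11.3.5 and 11.3.6 say the same of ECG, telemetry, laboratory and examination findings. The gap therefore concerns events that are reported by the subject, observed by staff or elicited by questioning (Section 11.3.1.11).

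**Effect of one subject whose only AE is pre-dose.** Section 9.3 gives 6 C106 and 2 placebo subjects per cohort, with six cohorts in Part A and four in Part B.

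- C106 cohort cell: 1/6 = 0.167, or 17 percentage points.
- Placebo cohort cell: 1/2 = 0.50, or 50 points.
- Placebo pooled over Part A: 6 × 2 = 12 subjects; 1/12 = 0.083, or 8 points.
- Placebo pooled over Part B: 4 × 2 = 8 subjects; 1/8 = 0.125, or 13 points.

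If the same subject also has a post-dose AE, any-AE incidence does not move, although an SOC or PT row may.

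**Distance from the baseline to the fed dose.** Sections 6.1.7 and 8.3.2 give an interim mean half-life of about 11 h. The minimum washout is then 5 × 11 h = 55 h, and 55/24 = 2.3 days. The baseline precedes the fasted dose, so it lies at least that far before the fed dose, with a dose in between. Part B has a single course of dosing and is unaffected.

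**Are the data for a fix collected?** Section 11.3.1.12 records, among other items, "start and stop dates, start and stop time; intensity; causal relationship to IMP; action taken, and outcome". Section 11.3.1.6 requires a start time for any AE that begins on a dosing day. Because Section 8.1.1.1 repeats the assessments, Table 8.1-2 yields new admission laboratory values and new pre-dose vital signs in the fed period. Onset and period can therefore be derived. Worsening is less secure, because no rule says how a change in intensity is recorded.

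**The case against.** The strongest reply is that the definition has only been deferred. Section 17 claims to give principal features, and says: "A more technical and detailed elaboration of the principal features will be presented in a separate Statistical Analysis Plan (SAP". That SAP is not in the supplied text and may define treatment emergence. This stands as a limit on the point. It does not remove it, because the endpoint and its analysis disagree within the protocol itself.

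The display also has safeguards. The overview shows relationship to IMP without condition, Section 11.3.1.8 makes implausible timing a ground for calling an event not related, and all AEs are listed. Pre-dose events should therefore not appear as drug-related. This stands, but total incidence would still include them.

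On the baseline, Section 17.1 presents results by assessment time, so a shift already present before the fed dose could be seen if those pre-dose values have their own row. That helps a careful reader, but the fed-period changes would still be measured from the wrong reference.

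A reader might infer more than the documents support:

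- **That pre-dose events will dominate the tables, because screening can last up to 28 days.** The documents give no background AE rate, and the time from screening to dose varies by subject.
- **That replacement subjects in the fed cohort fall outside the safety summaries, because the analysis set requires randomisation.** Table 8.1-1 schedules randomisation on Day 1 and no section exempts replacers. Nothing here calls for a new safety set.
- **That fasted and fed AEs will certainly be pooled.** Section 17.6.1 calls the feeding condition a cohort, while Section 8.1 uses the word for A4 itself. The wording is unclear, not decisive.
- **That dose escalation is affected.** Escalation rests on review by the internal safety review committee and the stopping rules in Sections 8.3.5 and 8.3.6, not on the Section 17.5.1 tables.

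**Conclusion.** The point holds in two parts and should be fixed.

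First, read as written, Section 17.5.1 counts pre-dose AEs of dosed subjects in the primary-endpoint tables. Each subject whose only AE is pre-dose adds 1/6 to a C106 cohort's any-AE incidence or 1/2 to a placebo cohort's. The number of such subjects is unknown.

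Second, the single baseline in Section 17.1 is wrong for the fed period of the food-interaction cohort, where it precedes the fed dose by at least about 55 h and an intervening dose. The 55 h rests on the interim half-life of 11 h and on the minimum washout; a longer washout lengthens it.

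These tables are descriptive and no formal test is affected, so the harm is to interpretation. The conclusion assumes that the separate SAP does not already settle both matters.

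**What to change.** - In Section 17.5.1, base the overview and the SOC/PT tables on AEs with onset at or after first IMP administration, and list pre-dose AEs separately. Add worsening of earlier conditions only if changes in intensity are recorded.
- In Section 17.1, for the food-interaction cohort, define each period's baseline as the latest value before that period's dose. Show AEs by period: from the fasted dose until the fed dose, and from the fed dose onward.
- Separately, reconcile the synopsis paragraph on food interaction, which brings back only subjects exposed to C106, with Sections 8.1.1.1 and 10.5.1, which include placebo. The answer decides whether the fed period has 6 or 8 subjects and whether it has a placebo comparison.

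The two analysis changes cost protocol and SAP wording before database lock. They use AE start dates and times and fed-period pre-dose values that are already collected, and need no new assessments.
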